7 DISCONTINUATION OF STUDY INTERVENTION AND PARTICIPANT DISCONTINUATION/WITHDRAWAL

Discontinuation of specific sites or of the study as a whole are detailed in Appendix 1 ([Section 10.1.9](#)).

7.1 DISCONTINUATION OF STUDY INTERVENTION

7.1.1 Permanent discontinuation

In rare instances, it may be necessary for a participant to permanently discontinue study intervention. If study intervention is permanently discontinued, the participant will have an early treatment discontinuation visit with all assessments planned for the EOT Visit. See the SoA ([Section 1.3](#)) for data to be collected at the time of early discontinuation of study intervention.

Definitive (permanent) discontinuation is any treatment discontinuation associated with the definitive decision from the Investigator not to re-expose the participant to the IMP at any time during the study, or from the participant not to be re-exposed to the IMP whatever the reason.

The participants may withdraw from treatment with the IMP if they decide to do so, at any time and irrespective of the reason, or this may be the Investigator's decision. All efforts should be made to document the reason(s) for treatment discontinuation and this should be documented in the eCRF.

Participants must be permanently withdrawn from the study treatment for the following reasons:

- At their own request or at the request of their legally authorized representative (legally authorized representative means an individual or judicial or other body authorized under applicable law to consent on behalf of a prospective participant to the participant's participation in the procedure(s) involved in the research)
- If, in the Investigator's opinion, continuation in the study would be detrimental to the participant's well-being
- At the specific request of the Sponsor
- In the event of a protocol deviation, at the discretion of the Investigator or the Sponsor
- Pregnancy
- Anaphylactic reactions or systemic allergic reactions that are related to IMP and require treatment (see Appendix 10 [[Section 10.10.5](#)])
- Severe intercurrent illness
- Diagnosis of a malignancy during study, excluding squamous or basal cell carcinoma of the skin
- Any opportunistic infection, such as TB or other infections whose nature or course may suggest an immunocompromised status (Appendix 10 [[Section 10.10.6](#)])
- Severe laboratory abnormalities:
 - Absolute neutrophil count $\leq 0.5 \times 10^9/L$

- Platelet count $\leq 50 \times 10^9/L$
- Serum ALT >3 ULN and total bilirubin >2 ULN
- Serum ALT >5 ULN if baseline ALT ≤ 2 ULN or ALT >8 ULN if baseline ALT >2 ULN
- Note: Any clinically significant abnormal laboratory value will be immediately rechecked for confirmation after 24 hours before making a decision of permanent discontinuation of the IMP for the concerned participant. If the laboratory abnormality is considered causally related to the IMP, the IMP will be permanently discontinued. In cases where a causal relationship to the IMP can be reasonably excluded (ie, an alternative cause is evident), the IMP will be discontinued but it may be resumed when the laboratory abnormality is sufficiently normalized.
- Occurrence of AEs, that, in the opinion of Investigator/Sponsor, may jeopardize participant's safety or data integrity
- Treatment with any prohibited systemic concomitant medication or procedure (see [Section 6.8.4](#))
- Treatment with any prohibited rescue medication or procedure (see [Section 6.8.5](#))

See the SoA ([Section 1.3](#)) for data to be collected at the time of definitive intervention discontinuation and follow-up and for any further evaluations that need to be completed. Any abnormal laboratory value or ECG parameter will be immediately rechecked for confirmation (within 48 hours) before making a decision of definitive discontinuation of the IMP for the concerned participant.

Handling of participants after permanent intervention discontinuation

Participants will be encouraged to remain in the study visits and to participate in all assessments according to schedule, up to the scheduled date of study completion, or up to recovery or stabilization of any AE to be followed-up as specified in this protocol, whichever comes last. Their study data collected during their continued involvement is important to the study efficacy analysis and study value.

If possible, and after the permanent discontinuation of intervention, the participants will be assessed using the procedure normally planned for the last dosing day with the IMP including a PK sample, if appropriate.

All cases of permanent intervention discontinuation must be recorded by the Investigator in the appropriate pages of the eCRF when considered as confirmed.

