7.1.2 Liver chemistry stopping criteria

Discontinuation of study intervention for abnormal liver tests is required by the Investigator when a participant meets one of the conditions outlined in Appendix 6 ([Section 10.6](#)) or in the presence of abnormal liver chemistries not meeting protocol-specified stopping rules if the Investigator believes that it is in best interest of the participant.

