7.1.4.1 Study intervention restart or rechallenge after liver stopping criteria are met

Study intervention restart or rechallenge after liver chemistry stopping criteria are met by any participant in this study are not allowed.

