8.3.8 Adverse events of special interest

An adverse event of special interest (AESI) is an AE (serious or nonserious) of scientific and medical concern specific to the Sponsor's product or program, for which ongoing monitoring and immediate notification by the Investigator to the Sponsor is required. Such events may require further investigation in order to characterize and understand them. Adverse events of special interest may be added, modified or removed during a study by protocol amendment. For AESI, the Sponsor is to be informed immediately (ie, within 24 hours), as per SAE notification guidelines, even if a seriousness criterion is not met, using the corresponding pages of the CRF (to be sent) or screens in the eCRF.

- Pregnancy of a female participant entered in a study as well as pregnancy occurring in a female partner of a male participant entered in a study with IMP:
 - Pregnancy occurring in a female participant entered in the clinical trial or in a female partner of a male participant entered in the clinical trial. It will be qualified as an SAE only if it fulfills one of the seriousness criteria (see Appendix 3 [Section 10.3]).
 - In the event of pregnancy in a female participant, IMP should be discontinued
 - Follow-up of the pregnancy in a female participant or in a female partner of a male participant is mandatory until the outcome has been determined (See Section 8.3.5)
- Symptomatic overdose (serious or nonserious) with IMP/NIMP
 - An overdose (accidental or intentional) with the IMP is an event suspected by the Investigator and defined as any administration of [REDACTED]
 - NIMP: any dose in excess of the maximum dose recommended in the respective medication labeling.
- Increase in ALT>3×ULN - see the "Increase in ALT" flow chart in Appendix 6 (Section 10.6).
- Other project specific AESI(s)
 - Systemic or localized allergic reactions that require immediate treatment (in the event that a participant has a systemic allergic reaction that requires immediate treatment, blood samples should be withdrawn as soon as feasible [not to interfere with treatment

of the reaction] for the analysis of ADA, serum tryptase, C1q, C1 inhibitor, C3 and C4, and repeated at 4 hours and 24 hours)

- Severe injection site reactions that last longer than 24 hours

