- a Details of liver chemistry stopping criteria and required actions and follow-up assessments after liver stopping or monitoring event are given in Appendix 6 ([Section 10.6](#)).
- b Local urine testing will be standard for the protocol unless serum testing is required by local regulation or IRB/IEC.

Investigators must document their review of each laboratory safety report.

10.3 APPENDIX 3: AES AND SAES: DEFINITIONS AND PROCEDURES FOR RECORDING, EVALUATING, FOLLOW-UP, AND REPORTING

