10.6 APPENDIX 6: LIVER AND OTHER SAFETY: SUGGESTED ACTIONS AND FOLLOW-UP ASSESSMENTS

*If unable to retest in 72 hours, use original lab results to decide on further reporting/monitoring/discontinuation.

** Unless a protocol-defined criterion for permanent discontinuation is met

*** See box below

Note:

[figure not shown]
“Baseline” refers to ALT sampled at baseline visit; or if baseline value unavailable, to the latest ALT sampled before the baseline visit. The algorithm does not apply to the instances of increase in ALT during screening.

See [Section 10.3.4](#) for guidance on safety reporting.

Evaluate Increase in ALT***

1. **INFORM** the Site Monitor who will forward the information to the Study Manager
2. **INVESTIGATE** specifically for malaise with or without loss of consciousness, dizziness, and/or hypotension and/or episode of arrhythmia in the previous 72 hours; rule out muscular injury
3. **INVESTIGATE** if any recent alcohol use or travel
4. **INVESTIGATE** if any use of non-prescription medications including herbal or dietary supplements
5. **PERFORM** the following tests:
 - LFTs: AST, ALT, alkaline phosphatase, GGT, total and conjugated bilirubin and prothrombin time / INR
 - CPK, serum creatinine, complete blood count
 - Anti-HAV IgM, anti-HBc IgM, (HBV-DNA if clinically indicated), anti-HCV and HCV RNA, anti-CMV IgM and anti-HEV IgM antibodies
 - Depending on the clinical context, check for recent infection with EBV, herpes viruses, and toxoplasma
 - Hepatobiliary ultrasonography (or other imaging investigations if needed)
6. **CONSIDER** Auto-antibodies: antinuclear, anti-DNA, anti-smooth muscle, anti-LKM
7. **CONSIDER** iron, ferritin and transferrin
8. **CONSIDER** biomarkers for alcohol use (eg, urine ethyl glucuronide (EtG)]
9. **CONSIDER** consulting with hepatologist
10. **CONSIDER** patient hospitalization if INR>2 (or PT<50%) and/or central nervous system disturbances suggesting hepatic encephalopathy
11. **MONITOR LFTs after discontinuation of IMP:**
 - *As closely as possible* (or **every 48 hours**) until stabilization, then every 2 weeks until return to \leq ULN, baseline value (if baseline >ULN) or clinical resolution.
12. **FREEZE** serum sample (5ml x 2)
13. **In case of suspicion of GILBERT Syndrome**, a DNA diagnostic test should be done

INCREASE IN CPK OF NON-CARDIAC ORIGIN AND NOT RELATED TO INTENSIVE PHYSICAL ACTIVITY

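### The resumption sentence in Protocol 7.1.1 reaches liver stopping values, for which 7.1.4.1 forbids restart, and 7.1.1 does not point to that bar

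*Protocol*

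**What the plan says.** Four parts of the Protocol bear on restarting study drug after a liver signal.

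- **Section 7.1.1, list.** Permanent withdrawal is mandatory for four lines of severe laboratory abnormality: neutrophils, platelets and two liver lines. The first liver line is "Serum ALT >3 ULN and total bilirubin >2 ULN". The second is ALT above 5 ULN, or above 8 ULN if baseline ALT exceeded 2 ULN.
- **Section 7.1.1, note after the list.** It covers any clinically significant abnormal laboratory value. It asks for a recheck after 24 hours and for permanent discontinuation if the abnormality is considered related to the IMP. Where an alternative cause is evident, "the IMP will be discontinued but it may be resumed when the laboratory abnormality is sufficiently normalized".
- **Section 7.1.2.** Discontinuation for abnormal liver tests is "required by the Investigator when a participant meets one of the conditions outlined in Appendix 6". Table 13, note a, also places the criteria there: "Details of liver chemistry stopping criteria and required actions and follow-up assessments after liver stopping or monitoring event are given in Appendix 6".
- **Sections 7.1.4 and 7.1.4.1.** Section 7.1.4 lets the IMP be reinitiated under close monitoring when the investigator judges the IMP unlikely to be responsible and the selection criteria are still met. Section 7.1.4.1, directly beneath it, says: "Study intervention restart or rechallenge after liver chemistry stopping criteria are met by any participant in this study are not allowed".

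**The concern.** The permission in 7.1.1 is general and the bar in 7.1.4.1 is absolute, and a participant with a liver stopping value and an evident other cause falls under both. The permission stands directly below the liver thresholds. The bar is three subsections further on, with no pointer to it. At stake is whether a participant with a marked rise in ALT, possibly together with bilirubin, is given study drug again when the protocol elsewhere says that this must not happen.

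**Working it through.** There is no figure to recompute. The check is a comparison of the texts.

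1. **Scope of the note.** It applies to any clinically significant abnormal laboratory value and makes no exception for liver tests.

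2. **Does a liver stopping value fall within that scope?** Yes. Section 7.1.2 requires the IMP to be discontinued when an Appendix 6 condition is met. Section 10.3.1 gives discontinuation of the IMP as one of its examples of what makes a laboratory abnormality clinically significant. Any Appendix 6 stop is therefore covered by the note, whatever its threshold.

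3. **What each rule says about the same participant.** Take a participant who meets an Appendix 6 stopping criterion. The Appendix 6 work-up includes viral hepatitis serology, alcohol history and imaging, so another cause may well come to light.

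| Question | 7.1.1 note | 7.1.4.1 |
|---|---|---|
| Stop the IMP now? | Yes | Presupposes that it was stopped |
| Does an evident other cause change the outcome? | Yes | No such exception |
| Restart after normalization? | May resume | Not allowed |

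4. **The two liver lines in 7.1.1.** Whether 7.1.4.1 also covers these depends on whether they match Appendix 6. The flow chart is not reproduced in the public text, so that cannot be confirmed. A surviving footnote, "Unless a protocol-defined criterion for permanent discontinuation is met", shows that the chart refers to the protocol's permanent-discontinuation criteria, but it gives no thresholds. Step 3 does not need this match.

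5. **Precedence.** Section 7.1.1 gives cross-references for several other reasons on its list (anaphylaxis, opportunistic infection, prohibited medication and rescue). It gives none to 7.1.2, 7.1.4, 7.1.4.1 or Appendix 6. Section 7.1.4.1 does not mention the note. No visible text says which rule governs.

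6. **What stands between the note and a re-dose.**
   - Section 7.1.3 treats two or more missed administrations as permanent discontinuation. This limits when a restart can occur but does not forbid one.
   - Section 7.1.4 requires close monitoring and that the selection criteria still hold. Criterion E 14 excludes ALT or AST above 2 times ULN, or bilirubin above 1.5 times ULN (with an exception for Gilbert's syndrome). E 14 is worded for Screening. If it is applied again at reinitiation, it gives some content to sufficient normalization. It does not reproduce the bar in 7.1.4.1.
   - ALT above 3 times ULN is an AESI: "For AESI, the Sponsor is to be informed immediately (ie, within 24 hours), as per SAE notification guidelines". ALT above 3 times ULN with bilirubin above 2 times ULN is listed as a medically important event in 10.3.2. The sponsor may also require withdrawal under 7.1.1. These give notice and a power to intervene. None is an approval step before a restart.

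7. **Frequency.** The documents give no rate for liver stops, no share with another evident cause and no share that normalizes in time. The number of conflict cases cannot be estimated and may be zero.

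**The case against.** The best answer is that the structure already orders the rules. Section 7.1.4 sets the general condition for reinitiation, which is in substance the condition in the 7.1.1 note. Section 7.1.4.1 follows as the liver exception, in absolute terms. A specific prohibition would normally override a general permission. The note is also only permissive, so a site that never restarts complies with both passages. And the Appendix 6 chart, which cannot be read here, might settle the matter.

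Much of this stands. The override reading is plausible and probably what was intended, and the conditions in 7.1.4 are real protection. But the protocol nowhere states that reading, and someone working from 7.1.1 is not sent to 7.1.4 or 7.1.4.1. The missing chart limits what can be said about the 7.1.1 thresholds and about precedence. It does not remove the overlap, because the note covers any liver stopping value.

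A reader might infer more: that the protocol endorses re-dosing after liver injury, that the 7.1.1 lines are known to be identical to the Appendix 6 criteria, or that participants were in fact re-dosed against the bar. The documents support none of these. The note permits and does not direct, the match of thresholds is unverified, and no case is described.

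**Conclusion.** The concern holds as a minor participant-safety inconsistency. On the visible text, a participant who meets a liver stopping criterion and has an evident other cause may resume under the 7.1.1 note and may not restart under 7.1.4.1.

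The conclusion rests on two readings: that the note means what it says in covering any clinically significant laboratory value, and that a liver stop is such a value. It does not rest on any particular Appendix 6 threshold. That no precedence is stated is established only for the text that can be seen.

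The frequency is unknown and possibly zero. No estimand, endpoint or analysis is affected.

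**What to change.** Leave the recheck and causality wording of the 7.1.1 note unchanged. Directly after the resumption sentence add: *Resumption is not allowed when the ALT/bilirubin criteria above or the liver chemistry stopping criteria in Section 7.1.2/Appendix 6 are met (see Section 7.1.4.1).*

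The addition should be limited to resumption. A sentence exempting liver values from the whole note would also remove their 24-hour recheck and the causality rule. The note stays in use for neutrophils, platelets and other laboratory values.

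Send the sentence to sites in a clarification letter while dosing continues, and align the protocol text if there is a further amendment. SAP 3.8 gives 22 April 2024 as the date by which all randomized participants had completed at least the Week 24 visit. The last dose, at Week 48, then falls nominally no later than 24 weeks (168 days) after that, 7 October 2024. This shows how long a letter is useful, not how often the conflict arises.

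The cost is one sentence, with no change to data collection or analysis. The downside is that a few participants with a clear non-IMP cause cannot restart. For Appendix 6 stops, 7.1.4.1 already requires that. If the 7.1.1 lines are broader than Appendix 6, the sentence slightly extends the bar, so the sponsor should compare the two sets before sending it.

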7.1.2 Liver chemistry stopping criteria

Discontinuation of study intervention for abnormal liver tests is required by the Investigator when a participant meets one of the conditions outlined in Appendix 6 ([Section 10.6](#)) or in the presence of abnormal liver chemistries not meeting protocol-specified stopping rules if the Investigator believes that it is in best interest of the participant.

7.1.3 Temporary discontinuation

Temporary intervention discontinuation may be considered by the Investigator because of suspected AEs or disruption of the clinical trial due to a regional or national emergency declared by a governmental agency (Appendix 9 [Section 10.9]: Contingency measures for a regional or national emergency that is declared by a governmental agency). For all temporary intervention discontinuations, duration should be recorded by the Investigator in the appropriate pages of the eCRF. Following a temporary interruption or missed dose, the IMP treatment should be reinitiated at the next scheduled visit, maintaining the original dose.

For the purpose of this study, a temporary discontinuation is defined as no more than 1 missed IMP administration. Two or more missed IMP administrations during the study will be considered permanent and relevant eCRF sections should be populated.

7.1.4 Rechallenge

Reinitiation of intervention with the IMP will be done under close and appropriate clinical and/or laboratory monitoring once the Investigator will have considered according to his/her best medical judgment that the responsibility of the IMP in the occurrence of the concerned AE was unlikely and if the selection criteria for the study are still met (refer to Section 5).

For a regional or national emergency declared by a governmental agency, contingency measures are included in Appendix 9 Section 10.9: Contingency measures for a regional or national emergency that is declared by a governmental agency.

7.1.4.1 Study intervention restart or rechallenge after liver stopping criteria are met

Study intervention restart or rechallenge after liver chemistry stopping criteria are met by any participant in this study are not allowed.

7.2 PARTICIPANT DISCONTINUATION/WITHDRAWAL FROM THE STUDY

- A participant may withdraw from the study at any time at his/her own request, or may be withdrawn at any time at the discretion of the Investigator for safety, behavioral or compliance reasons. This is expected to be uncommon.
- At the time of discontinuing from the study, if possible, an early discontinuation visit should be conducted, as shown in the SoA (Section 1.3). See SoA for data to be collected at the time of study discontinuation and follow-up and for any further evaluations that need to be completed.

Note: Safety follow-up (EOS, end-of-study) visit should be performed [REDACTED] after the last IMP.

- If the participant withdraws consent for disclosure of future information, the Sponsor may retain and continue to use any data collected before such a withdrawal of consent.
- If a participant withdraws from the study, he/she may request destruction of any samples taken and not tested, and the Investigator must document this in the site study records.

If participants no longer wish to take the IMP, they will be encouraged to remain in the study.

The Investigators should discuss with them key visits to attend. The value of all their study data collected during their continued involvement will be emphasized as important to the public health value of the study.

Participants who withdraw from the study intervention should be explicitly asked about the contribution of possible AEs to their decision, and any AE information elicited must be documented.

All study withdrawals should be recorded by the Investigator in the appropriate screens of the eCRF and in the participant's medical records. In the medical record, at least the date of the withdrawal and the reason should be documented.

In addition, a participant may withdraw his/her consent to stop participating in the study. Withdrawal of consent for intervention should be distinguished from withdrawal of consent for follow-up visits and from withdrawal of consent for non-participant contact follow-up, eg, medical record checks. The site should document any case of withdrawal of consent.

Participants who have withdrawn from the study cannot be rerandomized (treated) in the study. Their inclusion and intervention numbers must not be reused.

7.3 LOST TO FOLLOW UP

A participant will be considered lost to follow-up if he or she repeatedly fails to return for scheduled visits and is unable to be contacted by the study site.

The following actions must be taken if a participant fails to return to the clinic for a required study visit:

- The site must attempt to contact the participant and reschedule the missed visit as soon as possible, counsel the participant on the importance of maintaining the assigned visit schedule, and ascertain whether the participant wishes to and/or should continue in the study.
- Before a participant is deemed lost to follow-up, the Investigator or designee must make every effort to regain contact with the participant (where possible, 3 telephone calls, and, if necessary, a certified letter to the participant's last known mailing address or local equivalent methods). These contact attempts should be documented in the participant's medical record.
- Should the participant continue to be unreachable, he/she will be considered to have withdrawn from the study.
- If a participant continues to be unreachable and has been withdrawn from the study, the site should continue to try to obtain a vital status update (death) via available resources, if possible.

Discontinuation of specific sites or of the study as a whole are handled as part of Appendix 1 ([Section 10.1.9](#) Study and site start and closure).

